4.0 Study Endpoints

Outcome measures include cognitive (self-regulation); affective (emotional states); behavioral (social withdrawal, comfort eating); and physiological (cortisol secretion) responses to experimentally manipulated weight discrimination.

Measures to assess cognitive mechanisms.

Delay discounting task.⁹⁶ Delay discounting involves the subjective depreciation of an incentive based on its timing. The measure assesses the ability to delay gratification, that is, a tendency to prioritize larger long-term rewards over smaller short-term rewards. Participants will complete a well-validated task in which they choose short vs. long-term rewards from a set of five dichotomous choices (e.g., to receive \$1 immediately or \$10 in one month).⁹⁷ The task takes about 1 minute to administer, is highly reliable, and correlates well with longer and more extensive measures of delay discounting⁹⁷ (metric: discount rate (k) ranges from 0-1).

Stroop task. The Stroop task provides a measure of executive control by assessing the ability to inhibit an automatic response (reading) in favor of performing a more controlled task (color naming). The task is a classic, widely-used and well-validated measure of executive control.⁹⁸ Participants will perform 8 blocks of 20 trials that will take approximately 5 minutes to complete. Executive control scores will be calculated as a joint function of response accuracy and speed.⁹⁹

Measures to assess affective mechanisms. We will use a modified version of the Positive and Negative Affect Scale-Expanded Form (PANAS-X)¹⁰⁰ to assess emotions in response to the experimental manipulation. The scale demonstrates good validity and reliability.¹⁰⁰ Emotions will be assessed with 46 adjectives (e.g., angry, confident). Participants will be asked to indicate the extent to which they feel each emotion at that moment (1=very slightly or not at all to 5=extremely). A composite score for positive and negative emotion will be created by taking the average of the relevant adjectives.

Measures to assess behavioral mechanisms.

Social withdrawal. Social withdrawal will be assessed with a measure from previous research,⁵⁰ in which participants indicate the extent to which they want to work on a task either by themselves, with one of their former group members, or with a new partner. Choosing to work by oneself reflects a desire to avoid social interaction. The details of the task will be tailored for the study to fit the study's narrative flow.

Comfort eating. Comfort eating will be assessed via an eating task to objectively measure hyperpalatable (high-fat, -sodium, -sugar, and -carbohydrate) food intake.¹⁰¹ To avoid floor effects often observed in laboratory eating settings, the eating task will take place under the guise of a faux taste test.¹⁰² Participants will be asked to rate each of the

PROTOCOL TITLE: Decision Making Study

foods/drinks to ostensibly guide the development of their food marketing campaign later during the study. To avoid ceiling effects and to allow participants to eat without fearing that the experimenter will negatively judge the amount they have eaten, large quantities of each food will be made available. Participants will have 10 minutes to complete the task alone in a private room. Bowls will be weighed (unobtrusively) before and after the task to compute the difference in grams, which will then be converted to kilocalories based on published nutrition information from the food maker.

Self-efficacy for weight control behavior. Self-efficacy (perceived confidence) in one's ability to engage in weight control behaviors (e.g., dietary restraint, physical activity) over the next six months will be assessed with items adapted from previous research. Self-efficacy for dietary restraint will be assessed with the short form of the Weight Efficacy Lifestyle Questionnaire¹⁰³ (e.g., I can resist eating ... when I am depressed or down; 8 items). Self-efficacy for physical activity will be assessed with the Exercise Self-efficacy Scale¹⁰⁴ (e.g., I am confident I can participate in regular exercise when ... I am tired; 5 items). To mask the study's focus, weight control items will be interspersed with items assessing self-efficacy for other health behaviors (e.g., flu vaccination, sleep, cancer screening). Participants will rate their self-efficacy for each behavior on an 8-point scale (0=not at all confident to 7=very confident). Items will be averaged to create a composite score.

Intentions for weight control behavior. Using the same health behaviors assessed for self-efficacy, we will also assess intentions for weight control behavior. Participants will be asked to rate the extent to which they intend to engage in each behavior over the next six months.¹⁰⁵ Each item will be rated on an 8-point scale (0=strongly disagree to 7=strongly agree). Items will be averaged to create a composite score.

Measures to assess physiological mechanisms.

Cortisol reactivity. We will measure cortisol secretion via saliva (passive drool) at three timepoints during the session: baseline, 20 minutes post-manipulation (to assess reactions to the manipulation), and 60 minutes post-manipulation (to assess recovery).¹⁰⁶ As in previous research,¹⁰⁶ participants will be asked to swish their mouths with water 2-3 times before the final sample is collected to avoid altering cortisol levels. Within 2 hours of collection, saliva samples will be frozen at -20°C. As in our previous work,⁴⁸ samples will be analyzed in duplicate with immunoassays. Participants will be instructed to refrain from eating, drinking, smoking, or exercising for 1 hour before the session. To reduce diurnal cortisol variability, sessions will be conducted between 1:00 and 7:00 p.m. During the session, we will assess factors that could potentially affect assay results (e.g., consumption of food, alcohol, nicotine within the past 12 hours; presence of oral diseases or injury; current medications), so that we can control for them in analyses if needed.

Measures to assess moderators (Table 2). Moderators will be assessed with an online survey completed at least one week before the experimental session. We will use reliable and well-validated measures to assess all psychological moderators. Internalized weight bias will be assessed with the 11-item Modified Weight Bias Internalization Scale.⁷⁹ Self-compassion will be assessed with the 26-item Self-Compassion Scale.⁸³ The 60-item Big Five Inventory-2⁸² will be used to assess the five core personality domains (extraversion, agreeableness, conscientiousness, neuroticism, and openness). To mask the study's focus, the survey will include other measures unrelated to weight stigma (e.g., emotion

PROTOCOL TITLE: Decision Making Study

regulation),¹⁰⁷ plus demographic characteristics (e.g., education, biological sex) and health status (e.g., physical and mental health status, past medical history).

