Behavioral mechanisms. We will assess eating behavior, self-efficacy and intentions for weight control behavior, and social withdrawal. Numerous studies link weight discrimination to unhealthy eating behavior.³⁵ Exposure to weight discrimination is predicted to increase comfort eating as a means of immediate stress reduction.^{13,20,26,35,38,60} If left unregulated, however, comfort eating can promote further weight gain and impair cardiovascular health.⁶¹⁻⁶⁴ Additionally, exposure to weight stigma undermines self-efficacy for engaging in effective weight control behavior (confidence in one's ability to resist eating in certain situations).^{39,43,59,65} As these behaviors have important effects on weight,^{12,14,35} we will assess self-efficacy for weight control behavior and intentions to engage in healthy weight control behavior. Discrimination and social rejection also promote social withdrawal, a tendency to avoid social interaction in favor of social isolation.^{66,67} Although such isolation may bring temporary feelings of safety or relief, over extended periods, social withdrawal can promote loneliness, depression, and anxiety,⁶⁸⁻⁷⁰ which adversely affect cardiovascular health.⁷¹⁻⁷³ We hypothesize that exposure to weight discrimination will increase comfort eating, reduce self-efficacy and intentions for weight control behavior, and increase social withdrawal (Aim 1).

Physiological mechanisms. We will assess salivary cortisol, a steroid hormone that regulates the body's response to stress. Experimental work has demonstrated sustained cortisol reactivity in response to weight stigma (vs. control).^{44,45,74} Cortisol contributes to weight gain directly by promoting abdominal fat deposition and indirectly by promoting increased eating, especially hyperpalatable foods.²⁰ Over time, weight gain and obesity contribute to poor cardiovascular health.⁷⁵⁻⁷⁷ We hypothesize that exposure to weight discrimination will lead to increased cortisol reactivity (Aim 1).

Rationale for moderators (Aims 2 and 3).

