To assess cortisol (a steroid hormone that regulates the body's response to stress), participants will be asked to provide three saliva samples during the lab visit. The first saliva sample will be collected at baseline (5-10 minutes after they arrive at the lab). The second and third saliva samples will be collected 25 and 60 minutes, respectively, after delivery of the experimental manipulation. If participants finish all study measures before it is time to collect the third saliva sample, they will be asked to watch a video about marketing strategies to presumably help them prepare for the final task. Here's a link to the kind of video that will be shown to participants:

https://www.youtube.com/watch?v=0Ty64auIk_w

The experimenter will be instructed to stop the video when it's time to collect the sample.

We will use off-the-shelf foods for the taste test task. The following foods/drinks will be offered to participants: Lay's classic potato chips, Chips Ahoy cookies, milk chocolate M&M candies, and Sprite. During the taste test, participants will be provided with plentiful quantities of each food item (i.e., 80 grams of chips, 15 cookies, 300 grams of M&Ms) and 2 (355 mL) can of Sprite. These quantities were selected to circumvent both ceiling effects (i.e., participants eating all of the food available) and floor effects (i.e., participants eating no food at all) and are currently being used in a similar study being conducted by Co-I, [name]. All food items will be stored according to package instructions (e.g., in airtight containers to preserve freshness). Cans of Sprite will be refrigerated. Participants will not be given food items that have become stale or are beyond their "best by" date. Any expired foods will be discarded. For sanitary reasons, any food or drink that is leftover after the taste test will be discarded as soon as the research assistant has logged the post-task weight for each item.

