17.0 Data Management and Confidentiality

Statistical Design, Power, and Analysis Plan

We designed this study to have very high power for the main effects of weight discrimination (Aim 1) and to ensure sufficient sensitivity for moderation effects of psychological (Aim 2) and demographic variables (Aim 3).

➤ **Aim 1: Identify early-stage cognitive, affective, behavioral, and physiological mechanisms activated by experimentally manipulated weight discrimination.** We hypothesize that, relative to participants in the control condition(s), participants in the weight discrimination (experimental) condition (vs. control) will display more impaired self-regulation, higher negative emotion, lower positive emotion, more social withdrawal and comfort eating, lower self-efficacy and intentions for engaging in weight control behavior, and increased cortisol secretion.

Aim 1 power and analysis. Nine outcomes are assessed for the study (Table 1), hence we adopt a conservative Bonferroni adjustment when evaluating the primary hypothesis and use significance level $\alpha = 0.005$ to maintain familywise Type I error rate of 0.05. We assumed conservative effect size estimates, which were among the smallest observed in our pilot data.⁴⁸ We plan to recruit 160 subjects per condition for the study, which yields 90% power ($\alpha = 0.005$) to detect the medium Cohen's $d = 0.50$ between the control and experimental conditions.

Aim 1 analyses will use unadjusted ANOVA followed by analysis of covariance and multiple regression methods that permit adjustment for age and other baseline characteristics that may exhibit imbalance across experimental conditions. To analyze effects of the manipulation on cortisol secretion (assessed at 3 timepoints), we will calculate the area under the curve (AUC) with respect to ground (AUCg).¹²⁰ For all Aims, residual diagnostics will assess model assumptions (e.g., normality, homogeneity) and responses will be transformed if necessary. Effect of experimental weight discrimination will be reported for both unadjusted and adjusted analyses.

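### The AUCg cortisol outcome pools a pre-manipulation sample and a probably post-food sample, and baseline cortisol is not a named covariate; AUCg stays valid as total output but cannot be read as reactivity separate from eating

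*Combined protocol and SAP*

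**What the plan says.** **Sampling.** Section 4.0 places saliva samples at "baseline, 20 minutes post-manipulation (to assess reactions to the manipulation), and 60 minutes post-manipulation (to assess recovery" in each case. Section 6.0 gives a different time for sample 2: "The second and third saliva samples will be collected 25 and 60 minutes, respectively, after delivery of the experimental manipulation". On the first sample it says: "The first saliva sample will be collected at baseline (5-10 minutes after they arrive at the lab". The interval from that sample to the manipulation is not given.

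**Food.** The 10-minute taste test (chips, cookies, candies, soft drink, in plentiful amounts) is one of the outcome measures that follow the manipulation (Section 6.0). Section 4.0 asks participants to "swish their mouths with water 2-3 times before the final sample is collected to avoid altering cortisol levels", and asks this for no other sample. Section 6.0 provides a filler video "If participants finish all study measures before it is time to collect the third saliva sample". Section 3.0 states: "Exposure to weight discrimination is predicted to increase comfort eating as a means of immediate stress reduction".

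**Hypothesis and summary.** Section 3.0 states: "We hypothesize that exposure to weight discrimination will lead to increased cortisol reactivity (Aim 1". Sections 2.0, 4.0 (opening list) and 17.0 speak instead of cortisol secretion. For analysis, Section 17.0 says "we will calculate the area under the curve (AUC) with respect to ground (AUCg". It plans unadjusted ANOVA followed by models adjusting for age and for other baseline characteristics that may turn out imbalanced. Baseline cortisol is not named, and no separate analysis of sample 2 or sample 3 is described.

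**The concern.** Section 4.0 gives the three samples three roles: starting level, reaction and recovery. AUCg merges them into one number. Two consequences follow.

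- The baseline sample precedes the manipulation and cannot respond to it. In an unadjusted AUCg it contributes between-person variation and no signal.
- If the taste test comes before sample 3, that sample lies downstream of comfort eating, which is another Table 1 outcome and is predicted to differ by arm. The water rinse deals with residue in the mouth. It does not deal with any effect of eating on stress or secretion.

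At stake is the interpretation of the only physiological outcome. Aim 1 is meant to distinguish mechanisms. A null AUCg result could not be attributed to absent reactivity, and a positive one could not be separated from a response to eating.

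**Working it through.** **1. Order of food and sample 3.** No minute-by-minute schedule is given, so the order is inferred. The taste test is among the post-manipulation measures, the rinse applies to the final sample only, and the filler video covers people who have finished all measures before the third sample. Together these imply that food comes before sample 3 and suggest that it comes after sample 2.

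**2. The plan's own power figure.** Power = Φ(d√(n/2) − z), with n = 160 per arm, d = 0.50 and two-sided alpha 0.005 (z = 2.807; the plan does not state sidedness for Aim 1). √80 = 8.944, so Φ(0.50 × 8.944 − 2.807) = Φ(1.665) = 95.2%. The plan states 90%. The mismatch is conservative and does not affect this point.

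**3. Weights inside AUCg.** Assume 35 minutes from baseline sample to manipulation and sample 2 at 20 minutes. The times are then 0, 55 and 95 minutes. Trapezoid weights, as shares of the total:
- baseline: 55/(2 × 95) = 0.289
- sample 2: 95/(2 × 95) = 0.500
- sample 3: 40/(2 × 95) = 0.211

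With an assumed gap of 15 to 60 minutes and sample 2 at 20 or 25 minutes, the shares are 23–35%, 50% and 15–27%.

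**4. Effect sizes.** Assume equal SDs of 1, correlation 0.6 between all samples, no arm difference at baseline, 0.50 SD at sample 2 and m at sample 3.
- Numerator: 0.500 × 0.50 + 0.211 × m.
- Unadjusted variance: 0.6 + 0.4 × (0.289² + 0.500² + 0.211²) = 0.751, SD 0.867.
- Covariance of AUCg with baseline: 0.289 + 0.6 × 0.711 = 0.716.
- Variance adjusted for baseline: 0.751 − 0.716² = 0.239, SD 0.489.
- Sample 2 adjusted for baseline: d = 0.50/√(1 − 0.36) = 0.625, power >99%.

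| Sample-3 difference m (SD) | Numerator | AUCg unadjusted: d, power | AUCg adjusted for baseline: d, power |
|---|---|---|---|
| 0.50 | 0.355 | 0.41, 80.5% | 0.73, >99% |
| 0.25 | 0.303 | 0.35, 62% | 0.62, >99% |
| 0 | 0.250 | 0.29, 41% | 0.51, 96% |
| −0.25 | 0.197 | 0.23, 22% | 0.40, 79% |

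Sample 2 without adjustment has the 95.2% of step 2.

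**5. Sensitivity.** With a gap of 15–60 minutes, correlation 0.5–0.8 and sample 2 at 20 minutes, unadjusted AUCg has power 65–91% if eating has no effect at sample 3, 49–73% if eating halves the sample-3 difference, and 34–46% if it removes it. Adjusted for baseline, the lowest values over the same grid are >99%, 98.9% and 89%. Sample 2 adjusted for baseline has at least 99%.

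**The case against.** A reader might infer that AUCg is biased toward no effect and should be replaced by sample 2. The documents do not support that, for four reasons.

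- Under randomisation AUCg estimates the total effect of assignment on cortisol output, including any part that passes through eating. That is a legitimate quantity, and three sections of the protocol word the outcome as secretion, which a total measure fits. The baseline component dilutes the contrast but does not bias it.
- The protocol says that comfort eating serves stress reduction. It does not say that eating lowers salivary cortisol within the session, and it gives no size or direction for such an effect. The study cited for sampling and rinsing concerns stress reactivity and recovery after comfort foods, but its content cannot be checked here.
- Setting unadjusted AUCg (62%) against baseline-adjusted sample 2 (>99%) is not like for like. With both adjusted and the sample-3 difference halved, d is 0.62 against 0.625. With no food effect, adjusted AUCg does better (0.73).
- The 60-minute sample is deliberate, and the background cites sustained cortisol reactivity. Dropping it from the main outcome has a price.

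All four stand. It can also be said that Section 17.0 already allows adjustment for baseline characteristics. That stands only in part: baseline cortisol is not named, and the clause is tied to imbalance, whereas the gain in precision does not depend on imbalance.

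**Conclusion.** The point holds as a matter of interpretation and precision; it does not invalidate AUCg. As planned, AUCg cannot be read as stress reactivity separate from eating. Under the 35-minute assumption about 29% of its weight is pre-manipulation level and about 21% is the 60-minute sample.

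The larger and more certain loss is the unnamed covariate. With no eating effect at all, adjusting AUCg for baseline raises illustrative power from 80.5% to >99%. Leaving out sample 3 helps clearly only if eating removes or reverses its arm difference (96% or 79% for adjusted AUCg, against >99% for sample 2).

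The correlation, the baseline gap, the 0.50 SD difference and every sample-3 scenario are assumptions, since the documents give none of them. That food precedes sample 3 is a strong inference, not a stated fact.

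**What to change.** 1. In Section 17.0, name baseline cortisol as a covariate in the main cortisol analysis, whatever the observed balance.
2. Choose between secretion and reactivity wording for each cortisol analysis. Keep AUCg if total secretion is the target. Add a prespecified ANCOVA of sample 2 on baseline cortisol as the reactivity analysis.
3. Report the 60-minute sample separately as recovery after eating. Describe intake by arm, but do not adjust for it, because it is measured after randomisation and may itself be affected by the manipulation.
4. State in Section 6.0 that sample 2 precedes the taste test, and give the order of the taste test and sample 3.
5. Reconcile the 20 minutes in Section 4.0 with the 25 minutes in Section 6.0, since the choice changes the AUC weights.
6. Say which cortisol analysis counts among the nine outcomes. Nine tests at 0.005 use 0.045 of the familywise 0.05; a tenth at the same level would bring the total to 0.05.

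The cost is wording only. No extra samples or participants are needed, and the baseline sample is already collected.

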5.0 Study Intervention/Investigational Agent

The study intervention does not involve drugs or devices that are regulated by the FDA.

Participants will be randomly assigned to one of two conditions: experimental (weight discrimination) vs. control manipulation. The experimental manipulation will involve three components:

1. Learning that their groupmates are biased against overweight people
2. Receiving feedback that labels them with negative weight-based stereotypes (e.g., lacking self-discipline)
3. Not being selected as a partner for the remaining lab tasks (social exclusion).

In contrast, participants in the control condition will: 1) learn that their groupmates are very accepting of overweight people (i.e., they have positive attitudes toward people with higher body weight), 2) receive positive feedback about their personal attributes that are not consistent with negative weight-based stereotypes, and 3) will be told that one of their group members had to leave early for an emergency so the pairs cannot be assembled as usual (i.e., they will not experience social exclusion). In neither condition is any explicit reference to the participant's body weight, size, or shape included.

All three components of the planned experimental manipulation reflect common examples of weight discrimination reported by participants in our pilot data.^{46,47} Moreover, all three manipulations have been used in previous IRB-approved experimental studies involving weight stigma or social exclusion. **Interacting with a confederate/partner who is biased against overweight people (component 1)** has been used in published studies⁴¹ and is currently being used at UCLA for an NIH-funded study by Co-Investigator, [name], in concert with direct interaction with a confederate who expresses (veiled) negative stereotypes about the participant (we will not use this latter procedure in our study). **Giving people bogus feedback about their personal attributes has a long history in social psychology (component 2)**. Classic and recent studies, for example, have provided participants with bogus negative feedback about their intelligence.^{108,109} Similarly, studies have given participants bogus negative feedback about their level of competence to assess effects on psychological processes.¹¹⁰ Finally, the **group exclusion manipulation (component 3)** in which participants interact with a group and then learn that nobody chose to work with them has been used in many published studies,¹¹¹ including studies conducted at FSU by Co-Investigator, [name].^{50,112}

The study team used a combination of the second and third components a few years ago in a study in which participants received (bogus) negative feedback from their partner to manipulate weight stigma.⁴⁸ In (bogus) written feedback shared with the participant after viewing their video, a confederate (i.e., member of our study team who was pretending to be their partner for the study) indicated they were not looking forward to the face-to-face interaction with their partner (as indicated by a “2” on a 7-point scale ranging from 1 ‘not

PROTOCOL TITLE: Decision Making Study

at all' to 7 'very much'), and that they had a negative overall impression of their partner (as indicated by a "2" on a 7-point scale ranging from 1 'very negative' to 7 'very positive'). Their feedback also included the following hand-written note: "Her/His video was fine, but I guess I'm not that excited about talking face-to-face."

In summary, all components of the experimental manipulation used in the current study have been used in previous studies to produce immediate behavioral effects but, after thorough debriefing, no lasting distress or adverse effects have been reported.

Please see section 6.0 (Procedures Involved) for more detail about the experimental manipulation.

